## 1. Study Synopsis

Title of clinical trial	A prospective non-randomised control study to evaluate the efficacy of a physical activity promotion program on the experience of physical activity in patients with stage III and IV non-small cell lung cancer (NSCLC) with documented disease control ( stable disease, partial response or complete response defined by RECIST V1.1) after initial treatment
Protocol Short Title/Acronym	Monitoring and telecoaching of physical activity in patients with stage III and IV non-small cell lung cancer
Sponsor name	UZ Leuven
Principal Investigator	[name]. [name]
Medical condition or disease under investigation	Patients with stage III and IV NSCLC with documented disease control (stable disease, partial or complete response defined by RECIST V1.1) at least 6 months after start of first line treatment.
Purpose of clinical trial	
The objective of this pilot study is to investigate if physical activity can be improved by telecoaching in patients with advanced stages of lung cancer in remission.
 
The physical activity telecoaching promotion program is a personalized, coaching program using a direct measurement of physical activity to facilitate the semi-automated coaching.

Primary objective	
To assess the impact of a telecoaching program on physical activity in patients with stage III and IV NSCLC in addition to usual care. This will be measured by the Dynaport movemonitor (Dynamaport®), as the change in average daily number of steps at baseline (1 week preceding V3) and at the end (1 week preceding V4) in the intervention and the control group.

Secondary objective (s)	
The secondary objectives are to assess: Change from baseline to 8 weeks in the coaching program and the control group in:
 
 
• Change in health status assessed by QLQ-C30 (Cancer quality of life questionnaire)
 
• Change in exercise capacity by 6 minutes walking distance
 
 
Exploratory outcomes: Change from baseline to 8 weeks in the coaching program and control group.
 
 
• Comparison of change between coaching and control group in number of daily steps, in health status assessed by QLQ-C30 and in 6 MWT
 
• Time spent in at least moderate intense physical activity
 
• Walking time and intensity of moving during walking
 
• Symptoms and difficulties perceived during exercise (Pro Active questionnaire)
 
• Health related quality of life as measured by SGRQ.
 

Trial Design	A prospective non-randomised control study
Endpoints	The amount of steps per day objectively measured with Dynaport Movemonitor after 8 weeks

Sample Size	32 patients
Summary of eligibility criteria	
Inclusion criteria:
 
 
1. Patients diagnosed with stage III or stage IV NSCLC who have a documented disease control (stable disease, partial or complete response defined by RECIST V1.1) at least 6 months after start of first line treatment. Stage III patients can only be included, if first line treatment consisted of concurrent chemoradiotherapy and a consolidation immunotherapy if indicated (if PDL1 > 1% and no potential contraindications for immunotherapy). Stage IV patients, should have received only immunotherapy (PDL1 > 50%) or a treatment of at least 4 cycles of a platinum based chemotherapy. Maintenance therapy with chemotherapy and/or immunotherapy and administration of local radiotherapy is allowed. Patients with documented disease control can be included in the study until 2 years after starting up initial treatment.
 
2. > 18 years
 
3. Patients who are able to engage in a remote coaching program through the use of a smartphone
 
 
Exclusion criteria:
 
 
1. Patients actively participating in a pulmonary rehabilitation program
 
2. Patients with sequential chemoradiotherapy for stadium III non-small cell lung cancer
 
3. The presence of orthopedic problems not allowing an increase in PA levels
 

Maximum duration of treatment of a Subject	8 weeks
Version and date of final protocol	Version 5 (15-03-2019)

Version and date of protocol amendments	Version 5 amendment 15-03-2019)
---	---------------------------------

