#### **3.2 Primary endpoints**

To assess the impact of a telecoaching program on physical activity in patients with stage III and IV NSCLC with objective response (partial response or complete response defined by RECIST V 1.1) after initial treatment. This will be measured by the activity tracker (Dynaport movemonitor), as the change in average daily number of steps at baseline (1 week preceding V3) and at the end of the study (1 week preceding V4).

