#### **3.4 Exploratory endpoints**

1. The time in at least moderate intense physical activity
2. Walking time
3. Intensity of moving during walking

4. Symptoms and difficulties perceived during exercise (clinical version of the PROactive tool, C-PPAC)Active)
5. Health related quality of life as measured by SGRQ (St. George's respiratory questionnaire)
6. Change from baseline to 8 weeks between the telecoaching program and the control group in average daily number of steps, QLQ-C30 and 6 MWT.

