## **9 Statistics**

### **9.1 Sample size**

We will include 16 patients motivated for a coaching program and compare them with a matched control group of 16 patients receiving usual care. As this pilot study is underpowered to detect between group differences at the end of the intervention, we will base our primary analysis on the within group difference of the intervention group. Based on an anticipated pre-post difference of 1500 steps/day and a SD of 2000 steps/day, we need 16 individuals for a power of 80% using an  $\alpha$  level of 0.05 (two-sided, paired T test). The control group will be used to address the repeatability of the activity measures. Both groups will be needed for a power calculation of the subsequent randomized trial.

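### The primary objective claims an impact of telecoaching, but the primary analysis is a before-after test in the coached group alone; the objective needs rewording, the test does not

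*Protocol*

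**What the plan says.** - **Objective.** The Primary objective row of the synopsis (section 1) reads "To assess the impact of a telecoaching program on physical activity in patients with stage III and IV NSCLC in addition to usual care". The measure is the change in daily steps between the week before V3 and the week before V4, the latter described as "at the end (1 week preceding V4) in the intervention and the control group".
- **Primary endpoint.** Section 3.2 opens with "To assess the impact of a telecoaching program on physical activity in patients with stage III and IV NSCLC with objective response" and does not say in which group the change is taken.
- **Primary analysis.** Section 9.1 describes the pilot as underpowered between groups and then says "we will base our primary analysis on the within group difference of the intervention group". It plans to take 16 motivated patients and "compare them with a matched control group of 16 patients receiving usual care". The controls' stated roles are "The control group will be used to address the repeatability of the activity measures" and, together with the coached group, input to the power calculation for a later randomised trial.
- **Status of the comparison.** The synopsis lists "Comparison of change between coaching and control group in number of daily steps" among the exploratory outcomes. Section 3.4 does the same: "Change from baseline to 8 weeks between the telecoaching program and the control group in average daily number of steps, QLQ-C30 and 6 MWT". Section 9.2 plans an ANCOVA for it, adjusted for baseline and possible confounders.
- **Design label.** Section 3.1 calls the pilot uncontrolled. The synopsis and section 3.6 describe a non-randomised study with a control group.

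**The concern.** The objective determines what a positive result is taken to mean. Impact is a causal word, and here it stands beside usual care and a control group. A significant paired test in coached patients could then be reported as meeting that objective, although the test uses no control data.

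Two features of the design make the difference real. Both groups are given the activity brochure and discuss it at V3 (section 3.6), so a rise in steps among coached patients may partly reflect something the controls also received. Nor does anything in a one-group paired test separate coaching from other change over 8 weeks.

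At stake is the claim the pilot can make. Section 3.1 ties its result to whether a randomised trial is worth envisaging, so readers should know whether they are seeing change in coached patients or benefit over usual care.

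**Working it through.** **1. The plan's own figure.** Inputs from section 9.1: difference 1500 steps/day, SD 2000 (it must be the SD of the change for the stated n to reproduce), n = 16, two-sided alpha 0.05, paired t-test.
- Standardised effect: 1500/2000 = 0.75.
- Noncentrality at n = 16: 0.75 × √16 = 3.0, with 15 degrees of freedom and critical t = 2.1314.
- Power: 80.06%. Solving for 80% power gives n = 15.98, rounded up to 16.

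The stated sample size is correct for the paired test.

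**2. What the test responds to.** The smallest significant mean rise is t × SD/√n = 2.1314 × 2000/4 = 1066 steps/day. A rise above this is significant whatever caused it.

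**3. Illustration with no coaching effect.** The protocol gives no background change, so the shifts and the SD range below are assumptions. Noncentrality is shift × 4/SD; at SD 2000 it is 1.0 for a shift of 500 and 2.0 for a shift of 1000.

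| Assumed background rise (steps/day) | SD 1500 | SD 2000 (plan) | SD 2500 |
|---|---|---|---|
| 0 | 5.0% | 5.0% | 5.0% |
| 500 | 23.9% | 15.5% | 11.7% |
| 1000 | 70.3% | 46.5% | 32.2% |

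Each entry is the chance of a significant paired test. The figures hold for any single-arm before-after test of this size and would be the same after the objective is reworded. They show why the claim must be limited; they do not measure a fault in the test.

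**4. Would changing the test be the better remedy?** Take a between-group t-test on change with 16 per group, a difference of 1500 and, by assumption, an SD of change of 2000 in each group.
- Power is 53.7%.
- 80% power needs 29 per group (28.9 before rounding).
- The smallest difference detectable with 80% power is about 2050 steps/day.

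This bears out section 9.1's statement that the pilot is underpowered between groups. Extra patients would not remove the confounding that comes from the way patients enter each group.

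**5. The statements side by side.**

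| Place | What is primary | Place of the controls |
|---|---|---|
| Synopsis objective | Impact of coaching added to usual care | Named in the measure |
| Section 3.2 | Impact of coaching | Not mentioned |
| Section 9.1 | Before-after change in the coached group | Repeatability; powering the later trial |
| Synopsis exploratory outcomes, section 3.4 | Not applicable | Comparison with coached group is exploratory |

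The analysis section and the exploratory lists agree with one another. The wording of the objective is what does not fit.

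**The case against.** The strongest reply is that nothing conflicts. The phrase about usual care may only describe delivery: section 3.6 says coached patients receive usual care together with coaching, and section 3.1 uses the same phrase in a sentence that calls the study uncontrolled. Naming both groups may only say where steps are measured. Measuring two groups while powering one is compatible, the repeatability role needs control data at both times, and section 9.2 does not restrict paired tests to the coached group. Section 9.1 openly gives its choice and the reason, and section 3.1 claims no more than potential.

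Most of this stands. A reader might infer that the synopsis objective contradicts section 9.1 on every reading; the documents do not support that, because the delivery reading is a fair one. A reader might also infer that the wrong test was chosen, or that the plan intends to claim benefit over usual care from the paired test. The choice is disclosed, justified and consistent with the exploratory status of the comparison, and no passage announces such a claim.

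What the reply does not remove is the word impact, in both the objective and section 3.2. It is causal on any reading, and a one-group paired test cannot support it.

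**Conclusion.** The point holds as a fault in the stated objective, of minor to moderate severity. The primary test, n = 16 and the 80% power are sound for the question that section 9.1 asks: whether daily steps change in coached patients. They do not answer whether coaching has an impact.

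A reader might take 16% and 46% as this trial's false-positive rates. They are not. They rest on assumed upward shifts with no source in the protocol, and background change could equally be downward. The verdict does not depend on them. It rests on the text and on the fact that a one-group paired test does not isolate a cause.

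**What to change.** Keep the paired test and the 16 coached patients. Change the wording as follows.

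1. **Synopsis objective and section 3.2:** state the primary objective as the V3-to-V4 change in mean daily steps within the coached group, and give the control-group change the role section 9.1 assigns to it.
2. **Title and section 7:** bring the efficacy wording into line with that objective.
3. **Section 9:** state that no effect over usual care will be concluded from the paired test. State also that the ANCOVA already planned in section 9.2, reported with its 95% CI, is the only estimate relative to usual care. Label it exploratory and open to residual confounding despite matching and adjustment, because patients enter the groups by motivation (section 9.1), preference (section 6.1, Visit 3) and smartphone affinity (section 3.6).
4. **Section 3.1:** reconcile the uncontrolled label with the non-randomised controlled design named in the synopsis and section 3.6.

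No new patients, data or analyses are needed. The cost is a more modest headline: change in coached patients, with no conclusion of benefit over usual care.

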## 2. Background and rationale

Lung cancer has one of the highest mortality rates in both man and woman. The most common type is non-small cell lung cancer (NSCLC). When diagnosed, most of the patients have an advanced stage of lung cancer, which are not eligible for a curative intervention and can only be treated by chemotherapy or biologicals.

A vast majority of patients with advanced lung cancer experiences various impairments resulting from symptoms of the disease (like dyspnoea, coughing, fatigue, appetite loss) and side effects from the treatment affecting their quality of life. Today, long-term remission in advanced lung cancer is more frequently reached by the new targeted tumor therapies, often at the cost of a pronounced inactive lifestyle. Physical inactivity negatively influences the symptom burden, quality of life and likely prognosis, and should therefore be considered as an individual therapeutic goal. Factors contributing to the level of physical activity in lung cancer include patient-level factors, such as symptoms, comorbidities, sedentary lifestyle, mood and fear, and environmental factors.

For patients with lung cancer, exercise can be of contributory value. It increases strength and endurance and reduces fatigue. It may also help to decrease emotional issues following the diagnosis lung cancer and to better tolerate symptoms of the disease and its treatments. Whether a physical activity promotion program is effective in improving daily physical activity and whether this improvement leads to changes in quality is not yet demonstrated.

Stimulating home-based, low-intensity exercise monitored with a pedometer including behaviour strategies (goal setting, contracting, feedback, consequences and/or cues) has shown promising results to improve physical activity. Tele coaching interventions are attractive tools in this regard allowing remote communication and individual feedback through electronic devices like a smartphone and improving quality of life by treating patients in their own home environment and providing patients with independence by having them play an active role in their own treatment. Furthermore it is less time consuming and a cost-effective solution compared to usual care.

A few studies have been done to investigate the effectiveness of tele coaching in patients with cancer or cancer survivors. These studies showed that tele coaching is significantly more effective in increasing and maintaining moderate physical activity compared to usual care in cancer

survivors. As far as we know, there are no studies that focussed on tele coaching for improving physical activity in patients with lung cancer in particular. As most of these patients are also suffering from COPD , in which these interventions have been proven extremely effective , there is an obvious need to develop such programs.

The telecoaching program uses a previously developed coaching program, developed and validated by our research group in COPD patients. Briefly, the coaching will be facilitated by using a telecoaching system. Patients will be equipped with a step counter, which connects to a smartphone equipped with the needed coaching application.

Data from the stepcounter collected on the smartphone device will be shared using 'health care integrating information technology'.

### **3. Trial objectives and Design**

#### **3.1 Trial objectives**

The objective of this pilot study is to investigate if physical activity can be improved by telecoaching in patients with advanced stages of lung cancer in remission. We hypothesize that a smartphone application, designed for a population with respiratory symptoms, will increase daily physical activity, which translates into significant improvements on quality of life. This uncontrolled pilot study will therefore address if a 8-week PA promotion telecoaching program in addition to usual care has the potential to improve physical activity and quality of life in patients with lung cancer for a limited burden and at low cost. If so, a randomized controlled trial in a larger patient group can be envisaged.

#### **3.2 Primary endpoints**

To assess the impact of a telecoaching program on physical activity in patients with stage III and IV NSCLC with objective response (partial response or complete response defined by RECIST V 1.1) after initial treatment. This will be measured by the activity tracker (Dynaport movemonitor), as the change in average daily number of steps at baseline (1 week preceding V3) and at the end of the study (1 week preceding V4).

#### **3.3 Secondary endpoints**

1. Change in health status assessed by QLQ-C30 (*Cancer quality of life questionnaire*)
2. Change in exercise capacity by 6 minutes walking distance

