#### **QLQ-C30 (Cancer quality of life questionnaire)**

The QLQ-C30 is an internationally validated 30-item questionnaire assessing cancer-specific QOL. This widely used questionnaire comprises five functional scales (physical, social, role, cognitive and emotional functioning), 3 symptom scales (fatigue, pain, nausea and vomiting), a global health status/QoL scale, and a number of single items assessing additional symptoms commonly reported by cancer patients (dyspnea, loss of appetite, insomnia, constipation and diarrhea) and perceived financial impacts of the disease. Each linear converted scale score ranges from 0 to 100. High scores for functional scales and for the global health status/QOL indicate better functioning, whilst high scores for symptom scales represent a higher level of symptom burden.

The test takes about 10 minutes. A copy of the English version is attached in Appendix 1.

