### **9.2 Analysis**

Within group comparison of the primary and secondary outcome parameters will be analyzed by paired T-test statistics for parametric distributions and Wilcoxon signed-rank test test for non-parametric distributions. Linear and logistic regression will be used to address determinants of treatment response. Ancova analyses will be used to compare between group differences at 8 weeks, adjusted for baseline differences and possible confounders. Data will be presented as mean  $\pm$  SD. Statistical significance will be set at  $p<0.05$  for all the analyses.

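### Does the unnamed QLQ-C30 score, with p<0.05 for every analysis, let the quality-of-life hypothesis be met by chance?

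*Protocol*

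**What the plan says.** Section 3.3 and the synopsis list two secondary endpoints: the six-minute walking distance and "Change in health status assessed by QLQ-C30". Neither place says which score of the questionnaire is meant.

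The description of the instrument in section 3.4 says that it "comprises five functional scales (physical, social, role, cognitive and emotional functioning), 3 symptom scales (fatigue, pain, nausea and vomiting), a global health status/QoL scale". It adds single items for "dyspnea, loss of appetite, insomnia, constipation and diarrhea" and for "perceived financial impacts of the disease". On scoring it says: "Each linear converted scale score ranges from 0 to 100". No overall score is described.

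Section 9.2 compares primary and secondary outcomes within each group by paired t-test or Wilcoxon signed-rank test. On the level it says "Statistical significance will be set at" p<0.05, for all analyses.

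Section 3.1 hypothesises that the application "will increase daily physical activity, which translates into significant improvements on quality of life". It asks whether the program has the potential to improve activity and quality of life and, if so, allows that a randomised trial could be considered. Section 9.1 places the primary analysis on the within-group change in the intervention group and uses the control group to study the repeatability of the activity measures.

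**The concern.** The study hypothesis speaks of significant improvement in quality of life, and the QLQ-C30 is the secondary endpoint that bears on it. With 15 scores, no score designated and one nominal level for everything, the protocol's wording does not stop an analyst from picking the most favourable score after seeing the data. A reader of the report could not then tell a planned result from a chance one. Because quality of life is mentioned where the protocol looks ahead to a randomised trial, a spurious finding might help to justify that trial.

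**Working it through.** **The plan's own figure.** The protocol gives no error rate for the QLQ-C30. The related figure it does give is the sample size. With a mean change of 1500 steps and an SD of 2000, d = 1500/2000 = 0.75. Power of a two-sided paired t-test at 0.05, from the noncentral t distribution, is 77.1% at n = 15 and 80.06% at n = 16. The stated 16 patients for 80% power is reproduced.

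**Number of scores (section 3.4).** 5 functional + 3 symptom + 1 global + 5 single symptoms + 1 financial item = 15.

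**Inputs for the error rate.** Level 0.05 (section 9.2). Two-sided testing is stated in 9.1 for the sample size and is assumed here for the secondary tests. n = 16 in the intervention group. The correlation between the changes in the 15 scores is not in the protocol, so it is shown as a range.

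**Formulas for independent scores.**
- Any significant change, either direction: 1 − 0.95^15 = 0.537.
- Any significant improvement: 1 − 0.975^15 = 0.316.

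**Correlated scores.** Simulation of 15 equicorrelated normal changes, one-sample t-tests, n = 16, 40,000 null trials per value:

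| Correlation | Either direction | Improvement only |
|---|---|---|
| 0 | 53.6% | 31.8% |
| 0.3 | 46.8% | 24.5% |
| 0.5 | 37.5% | 18.9% |
| 0.7 | 27.0% | 13.6% |

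**Which column applies.** The hypothesis is about improvement, so the right-hand column is the relevant one. Counting significant worsening as support roughly doubles the rate. Against 2.5% for one pre-named score, the inflation is 0.136/0.025 = 5.4 to 0.316/0.025 = 12.6 times.

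**Which arms count.** Testing both arms would give 30 tests and 1 − 0.95^30 = 0.785 under independence. That figure does not bear on the hypothesis: an improvement under usual care is no evidence for telecoaching, and 9.1 gives the control arm a different purpose.

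**What the figures presuppose.** They need two rules: all 15 scores are tested, and any one significant improvement carries the conclusion. Sections 3.1, 3.3, 3.4 and 9.2 contain neither. Section 9.2 says how outcome parameters are compared, not how many QLQ-C30 parameters there are. Section 3.1 asks about potential and attaches no p-value to a later trial. It also asks for activity and quality of life together, so a lone chance subscale would not satisfy it, although this protects only where steps do not improve.

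**The case for a change.** The best case for a change is that the identity of an endpoint belongs in the protocol, and that this protocol accepts as much elsewhere. From several activity-monitor outputs it picks mean daily step count as primary and lists the others as exploratory, and for the walk test it takes the best of two attempts. It describes a total score for C-PPAC and SGRQ, both of them exploratory. The QLQ-C30 is the only secondary endpoint left open, and it has the most scores. Nor does the term health status settle the matter: section 3.4 has a global health status/QoL scale, but it uses the same term loosely for what the SGRQ measures. Naming one score would take a sentence and need no new data.

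Much of this stands. The count of 15 is right, no score is designated, and the inflation under an any-one-score rule is real. Two things do not follow. The protocol does not adopt that rule, so the rates describe a possible misuse and not the plan. And the choice of score is not obvious: global health status is one candidate, but physical functioning or fatigue may lie closer to what an activity program changes. Statisticians also differ on whether nominal secondary tests in a pilot should be restricted at all. These are choices for the analysis plan, not errors in the protocol.

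**Conclusion.** No change to the protocol follows. The endpoint is under-specified, and if it were abused by testing all 15 scores in the coached group and accepting any improvement, about 14% to 32% of null trials would show one. That range assumes equicorrelated normal changes with correlation 0.7 to 0, 16 complete patients and two-sided tests at 0.05. But the protocol states no such rule, the endpoint is secondary, and no go/no-go decision hangs on its p-value. Which score to analyse and how to treat multiplicity among secondary outcomes are details commonly settled in a statistical analysis plan, which may exist here but is not shown. An analyst would sensibly choose the score there before seeing the data and report the rest with confidence intervals. The primary analysis of daily steps and its sample size are unaffected.
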